#### Interventions:

After recruitment and consent, patients will be 1:1 randomized to receive:

1. **PICC:** Bard 3fr, 4fr or 6fr; Cook 4fr; or Medcomp 1.9fr and 2.6fr. (type and size to be selected based on interventional radiology standard protocol)

2. LPC: Bard Powerglide 8 cm, 20G and 22G. (size to be selected based on patient size)

## F. Research procedures such as lab draws (including volume of samples), ECG, imaging, clinical procedures, genetic testing, surveys (may attach activity table if available):

The participants will enroll in the study prior to VAD placement; however, this procedure is based on clinical indications and part of routine care, so it is not a research procedure. The only research procedure for this study is the semi-structure interview and pain/anxiety assessments (see section on data analysis on section 6)

#### Describe what will happen to the subject solely for the purpose of this research study:

The **child participant** will undergo randomization, prospective health data collection, and pain/anxiety assessments related to VAD placement (1 anxiety survey before and 1 repeat anxiety survey with pain rating after VAD placement) solely for the purpose of this study.

The **adult participant (parent/guardian)** would complete anxiety assessments related to their child's VAD placement (1 survey before and 1 repeat survey after placement) and agreement to participate in a semi-structured interview after the VAD is removed. The child participant is welcome to contribute to the semi-structured interview responses with the parent as a child-parent dyad, but the child is not required to do so as part of the study.

The parent and child will be given the first survey to fill out prior to VAD placement. The study team member will distribute and collect the first survey. The repeat survey will be placed in the patient's binder. Following VAD placement (and once child is fully alert if sedation was used during placement), the study team member will either (1) return to distribute the repeat surveys to the family, or if unable (e.g. VAD is placed after business hours) (2) will Voalte the bedside nurse to hand the repeat survey papers to the guardian and child, and store them in the patient's binder upon completion. The study team member will collect the second completed surveys from the families. The study team member will enter the paper survey data into the REDCap database form associated with the participants, and then shred the paper versions. **Describe what is happening per protocol but is considered part of routine care (would happen even if the individual did not participate):** 

VAD placement is part of the routine care for the population of interest (hospitalized children with given inclusion/exclusion criteria). All participants would receive a VAD (specifically a PICC) for vascular access even if they did not participate in the study. What the study offers is the opportunity to receive a different VAD (an LPC) that is also routine care just like the PICC, but may have a few benefits compared to PICCs This allows for comparison of those two VADs to determine which has the best effectiveness and safety profile making it the better option for vascular access. Per adult literature and a few studies in pediatrics (including our own local preliminary data), LPCs are safer than PICC regarding complications such as clots and line infections; however, they may not last as long as PICCs. Randomization to the LPC arm could pose the risk of early catheter failure (e.g., due to dislodgement) needing replacement of the VAD. Replacing the VAD will cause an additional poke for the patient (similar to replacing a peripheral IV).

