days,[14,21–24,26,27] supporting their use for medium-term vascular access. Second, LPCs tend to have fewer significant complications compared to PICCs, aligning with findings in the adult literature. In one study, PICCs were associated with more complications during placement while LPCs had more complications during use.[22] A second study, a retrospective review of neonatal cases, showed that LPCs had no lifethreatening complications while PICCs were associated with 4 life-threatening events during the study Form Version Date: 02/24/2020 CW Protocol Summary Page 3 of 30

period.[14] Both studies were completed using retrospective analysis of electronic medical records (EMR), so more rigorous study designs comparing PICCs to LPCs are still needed. The feasibility of a randomized clinical trial comparing PICCs to LPCs in children with cystic fibrosis was proven possible in an Australian pediatric center, with a reduction of general anesthesia use for VAD placement (69% in PICCs vs 10% in LPCs).[19]

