#### Risks

A. Describe potential research-related risks and discomforts (consider physical, psychological, legal, social/economic/financial, loss of confidentiality, group harms); describe the probability, magnitude, and duration of the potential risks; do not address risks that would be present if the individual did not participate:

Physical risks: The subjects included in this study require VADs for medical treatment, which poses risks for complications and hospital-acquired conditions. Since it is not yet clearly known whether one VAD is more effective than the other in pediatric patients, the research randomization process could introduce physical risks that may not have occurred if the opposite VAD was selected by the medical team.

(1) Based on available literature, LPCs are safer than PICCs with fewer significant side effects (VTE, CLABSI) because they don't enter the central circulation. However, because LPCs are peripheral VADs (similar to a regular peripheral IV) they may not last as long as a PICC. Patients randomized to the LPC arm may be at higher risk for needing VAD replacement due to early catheter failure.

(2) VADs are sometimes used for lab draws to avoid extra poke to the patient. Both PICCs and LPCs can be used for lab draws; however, it is unknown if LPCs can sustain as many lab draws as PICCs before catheter failure.

(3) Most PICCs are placed under sedation while LPCs are placed awake. Randomization to the LPC arm would prevent the risks associated with sedation (e.g., nausea/vomiting, confusion). However, because the LPC will be placed in an awake patient (similar to a regular peripheral IV), there would be pain/discomfort with the placement, but this discomfort would be short lived (most discomfort is while the needle is inserted which takes a few seconds) and minimized using established comfort measures. Any other physical risks are expected to be comparable to ordinary medical care.

Psychosocial risks: Subjects and their guardians may feel discomfort participating in the structured interview about their experience with the VAD. Discomfort could arise from recalling stressful experiences during the child's hospitalization. These risks are expected to be comparable to ordinary life.

Privacy risks: Data security breaches could risk a loss of privacy for subjects included in this study.

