#### D. Describe procedures to be employed in analyzing data (including a power analysis):

Quantitative. Study data will be collected using REDCap. Feasibility outcomes will be collected from (1) screening logs maintained by the study team (rate of enrollment, assigned intervention), (2) ease/difficulty of VAD placement (scale 0=worse to 10=best) to determine VAD acceptability, and (3) REDCap datasheet for assessing missed data. Patient demographics (age, gender, race/ethnicity), clinical factors (reason for admission, co-morbidities, reason for PICC/LPC request, therapy to be infused, requesting service, hospital floor), VAD data (VAD type and size placed, insertion site/vessel, sedation, number of attempts, additional VADs), effectiveness data (time-to-removal of VAD, prolonged NPO, number of lab draws from VAD, number of non-VAD blood draws) and complications requiring medical intervention will be collected using the EMR and daily (Monday-Friday) check-ins with the bedside nurse. Procedural pain with non-sedated VAD placement will be assessed in patients age > 5 years by the RC within 24 hours of insertion using the Faces Pain Score (FPS) or the 0-10 pain scale depending on the developmental age of the patient. Patient/parent anxiety and overall experience with VAD placement will be assessed on a 0-10 scale (0= lowest, 10=highest) and using the short State-trait anxiety inventory (STAI) that is validated in children 5 and older.

Descriptive statistics will be used to report feasibility outcomes and explore clinical factors (see above). Cross over rate will be calculated as the proportion of the number of subjects who crosses from the randomized arm/line to a different arm/line. The exact Clopper-Pearson 95% confidence interval will be generated. Time-to-device removal for all reasons will be compared using a t-test. Non-inferiority of LPCs to PICCs will be demonstrated if the 95% confidence interval of the mean difference lies above -1 (non-inferiority margin: 1 day). The remaining outcomes will be compared using Chi-square test or Fisher's exact for categorical variables and t-test or Mann-Whitney-Wilcoxon test for continuous variables. Where necessary for parametric assumptions, appropriate transformations will be employed. Non-parametric tests will be used where parametric assumptions are not satisfied. Logistic regression or general linear model will be performed to control the potential confounders.

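### The repeat anxiety surveys have no common time window, the wait for alertness falls mainly on the PICC arm, and the pre-placement score has no stated use in the analysis

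*Combined protocol and SAP*

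**What the plan says.** **Survey schedule (Section 1 F).** The child has "1 anxiety survey before and 1 repeat anxiety survey with pain rating after VAD placement"; the parent likewise has one survey before and one after. The repeat surveys are released "Following VAD placement (and once child is fully alert if sedation was used during placement". A study team member returns with the forms or, "if unable (e.g. VAD is placed after business hours) (2) will Voalte the bedside nurse to hand the repeat survey papers". Answers are then entered in REDCap and the paper is shredded. No number of hours is given for the repeat survey, and no time of completion is listed among the data.

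**Sedation by arm.** Section 1, Risks, states: "Most PICCs are placed under sedation while LPCs are placed awake". Table 1 and the risk-level rationale in Section 8 agree. The only figures are in the background (Section 1 D), from an external feasibility trial in cystic fibrosis: "with a reduction of general anesthesia use for VAD placement (69% in PICCs vs 10% in LPCs".

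**Measures (Section 6 D).** "Patient/parent anxiety and overall experience with VAD placement will be assessed on a 0-10 scale", and also "using the short State-trait anxiety inventory (STAI) that is validated in children 5 and older". A time limit appears only for pain: "Procedural pain with non-sedated VAD placement will be assessed in patients age > 5 years by the RC within 24 hours of insertion".

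**Analysis (Section 6 D).** Continuous outcomes other than time to removal go to a t-test or a Mann-Whitney-Wilcoxon test. A logistic or general linear model for confounders is also mentioned, without naming any covariate. The pre-placement anxiety score has no stated role. Aim 3 (Section 1 C) is to describe patient and parent distress.

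**The concern.** Anxiety around a procedure may change in the hours after it. If so, when the question is asked is part of what the score measures. Here one arm mostly waits for recovery from sedation and the other does not, so elapsed time is tied to the randomized device. The parent is affected too: the parent is not sedated, but the family's forms are released together once the child is alert.

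A difference in post-placement anxiety could then mix the effect of the device strategy with the effect of when the question was asked. If completion times are not captured before the forms are destroyed, nobody can check this afterwards.

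There is also a loss of precision. A pre-placement score is collected, and a two-sample test on the post-placement score ignores it.

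**Working it through.** The plan states no figure on survey timing, so there is none to reproduce. The illustration below uses the plan's sample size and its cited sedation figures; every other input is marked as assumed.

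**1. Timing rules side by side**

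| Placement | Release condition | Upper limit |
|---|---|---|
| Sedated (mainly PICC) | after placement and once fully alert | none stated |
| Awake (LPC, some PICC) | after placement, by study team or nurse | none stated for anxiety; 24 hours for the pain rating (age > 5), which accompanies the child's repeat survey |

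The extra condition applies only to sedated placements. Nothing fixes a prompt time for awake ones.

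**2. Possible shift in the arm difference**

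Shift = (share sedated, PICC − share sedated, LPC) × d, where d is the mean change in anxiety over the extra wait. The documents do not give d; 0 to 2 points on the 0-10 scale is assumed.

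| Shares | d = 0 | d = 0.5 | d = 1 | d = 2 |
|---|---|---|---|---|
| 69% vs 10% (external trial, general anesthesia) | 0 | 0.29 | 0.59 | 1.18 |
| 100% vs 0% (extreme) | 0 | 0.5 | 1.0 | 2.0 |

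A steeper set of assumptions is a change of 0.3-0.6 point per hour over a wait of 2-4 hours. Then d runs from 0.3 × 2 = 0.6 to 0.6 × 4 = 2.4. At 69% vs 10% the shift is 0.59 × 0.6 = 0.35 to 0.59 × 2.4 = 1.4 points. A shift of 0.6 to 2.4 needs every PICC and no LPC to be sedated.

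**3. Precision for comparison**

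With 35 per arm (Section 3 A), the 95% half-width of a mean difference is 1.96 × SD × √(2/35) = 0.47 SD. With an assumed SD of 2.5 points this is 1.17 points. It assumes all 70 children or parents give a score; fewer would widen it.

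The shift can therefore be nil, or about as large as the half-width. The documents give no wait, rate of change or SD to decide between these.

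**4. Value of the pre-placement score**

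A linear model with arm and pre-score multiplies residual variance by 1 − r², where r is the pre-post correlation (not in the documents; 0.5-0.6 assumed).

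- r = 0.5: 1 − 0.25 = 0.75, a 25% reduction, equivalent to 1/0.75 = 1.33 times the sample.
- r = 0.6: 1 − 0.36 = 0.64, a 36% reduction, equivalent to 1/0.64 = 1.56 times the sample.

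**The case against.** A reader might infer that the comparison *is* biased, and that it will make LPC families look more anxious because they answer sooner. The documents do not support that.

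- **Size and direction are unknown.** Both depend on assumed inputs, and zero change over the wait is possible. Parents might equally be more anxious around sedation and recovery.
- **Awake families are not told to answer at once.** The study team returns when it can, or the nurse hands out the forms, in either arm. Since the pain rating comes with the child's repeat survey, awake children may plausibly answer at any point within 24 hours.
- **The alertness condition is needed.** A sedated child cannot give a valid self-report. Aim 3 also covers distress from sedation, so recovery is arguably part of the experience studied. Equal hours since placement would still leave sedated children nearer to waking.
- **The momentary-state premise is not certain.** The survey wording is not in the documents, so the 0-10 item may ask about the procedure in retrospect.
- **The plan is not confined to two-sample tests.** It mentions a general linear model, and a model with the pre-score is one.
- **The stakes are low.** The outcome belongs to Aim 3 of a pilot that is not powered for significance.

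All of this stands, and it limits the point to a possible distortion. It does not supply a common window, a record of elapsed time, or a named covariate. Describing Aim 3 does not settle it either, because Section 6 D says remaining outcomes will be compared and makes no exception for anxiety.

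**Conclusion.** The point holds in a limited form. Time since placement can differ systematically between arms, because a condition tied to sedation falls mainly on PICC placements and no common window is set. This could distort the anxiety comparison, and the plan as written could not show whether it had. Separately, the collected pre-placement score has no stated use.

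The illustrated shift of 0 to 1.18 points rests on an assumed change over the wait and on general anesthesia shares from a different population. The precision gain rests on an assumed correlation. Neither is an estimate for this trial. The point is minor. It still deserves correction, because the pilot is meant to test the protocol for a full-scale trial and an untimed survey could be carried forward.

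**What to change.** 1. **Analysis.** In Section 6 D, state that the post-placement anxiety score will be analysed with a linear model containing arm and the pre-placement score, among participants who have both. Children under 5 need a stated rule for the short STAI, since enrolment starts at age 2 and the plan describes validation only from 5. The plan does not say whether the first survey precedes disclosure of the assignment. It should, so that the score is a true baseline.
2. **Timing.** Keep the alertness condition. Set one post-placement window for both arms, long enough for sedated children to recover and within 24 hours.
3. **Recording.** Enter the times of placement and survey completion in REDCap before the paper is shredded, and report elapsed time by arm. If the arms differ, add elapsed time as a sensitivity covariate only: it will be closely tied to arm, so the adjusted estimate may be imprecise.

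The cost is one survey instruction, two time stamps and one or two analysis sentences. The downside is that LPC families may answer somewhat later than they would have, and one window does not remove every difference linked to sedation.

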#### **Clinical Trial**

#### A. Is this study a Clinical Trial/Clinical Investigation?

**Clinical Trial** means a research study in which one or more human subjects are prospectively assigned to one or more interventions (which may include placebo or other control) to evaluate the effects of the interventions on biomedical or behavioral health-related outcomes. [45 CFR 46.102(b)]

*Clinical Investigation* means any experiment that involves a test article and one or more human subjects, and that either must meet the requirements for prior submission to the Food and Drug Administration under section 505(i) or 520(g) of the act, or need not meet the requirements for prior submission to the Food and Drug Administration under these sections of the act, but the results of which are intended to be later submitted to, or held for inspection by, the Food and Drug Administration as part of an application for a research or marketing permit. The term does not include experiments that must meet the provisions of part 58, regarding nonclinical laboratory studies. The terms research, clinical research, clinical study, study, and clinical investigation are deemed to be synonymous for purposes of this part. [21 CFR 56.102(c)]. Note: this also include biospecimens.

 $\Box$ No If NO, skip questions B-H  $\boxtimes$  Yes If YES, answer the following questions B-H:

В.	What phase of clinical trial best describes this research?
	Phase I Phase I/II Phase II Phase II/III Phase III Phase IV
	Feasibility      Pivotal ( Feasibility vs Pivotal device studies )
C.	Is this trial "first-in-human" (in clinical trials, the first Phase-1 study in which a test product is administered to human beings)?
	🖾 No 🔲 Yes
	If YES, the protocol must contain an adequate description of the pre-clinical research and/or other relevant data that supports the performance of the study.
D.	Is this trial the first in a population (e.g., children)?
	⊠No □Yes
	If YES, the protocol must contain an adequate description of the pre-clinical research and/or other relevant data that supports the performance of the study in the new population.
E.	Does this trial evaluate one or more FDA-regulated products?
	Human Cells, Tissues, and Cellular and Tissue-Based Products (HCT/P's) may be classified as drugs, devices, and/or biologics. Information on the classification of HCT/P's is available on this FDA website .
	The 21 st Century Cures Act excludes certain medical and decision support software from the definition of medical device meaning that such software is not subject to FDA regulations. Information regarding these exclusions is available on FDA's website for digital health . If uncertain whether a product under investigation is a medical device, contact the CW HRPP office.
	□No If YES, indicate the following:
	Product Type(s): Vascular access devices
	Product Name(s): 1) Peripherally Inserted Central Catheters: Bard 3fr, 4fr or 6fr; Cook 4fr; or Medcomp 1.9fr and 2.6fr. (type and size to be selected based on interventional radiology standard protocol)
	2) Long Peripheral Catheters: Bard Powerglide 8 cm, 20G and 22G. (size to be selected based on patient size)
	If YES, also include in the submission package IRB – Supplement Form – Drugs and Biologics for studies of drugs and biologics and/or IRB – Supplement Form – Devices for medical device studies. These forms are found in IRBNet under Forms and Templates.
F.	Will this trial enroll pregnant women or minors/women who are of child-bearing potential?
	If YES , the protocol and consent must contain an adequate description of any known or anticipatable risks to pregnant women and fetuses and any measures to mitigate those risks. Birth control requirements, if applicable, must also be described. CW template pregnancy test language regarding disclosure of results must be included in parental permission/assent documents.
G.	Does the sponsor intend to collect data on "pregnant partners" (sexual partners of clinical trial subjects who become pregnant while the subject is receiving investigational agents)?

#### ⊠No □Yes

**If YES**, review Children's Wisconsin IRB Position Statement Pregnant Subjects and Pregnant Partners found in IRBNet under Forms and Templates and on the HRPP web pages.

#### H. Is this trial registered in ClinicalTrials.gov?

Contact MCW CTSI if there are questions about what needs to be registered or visit their website for registration instructions.

#### **N/A**, registration is not required for this trial (confirm with CTSI if uncertain)

**No, but trial will be registered prior to enrolling any subjects** 

**Yes, ClinicalTrials.gov #:** NCT05346406

For FDA-regulated and NIH funded clinical trials that are or will be registered in ClinicalTrials.gov, the following statement must be included verbatim in the consent/parental permission forms:

#### FDA: "A description of

this clinical trial will be available on http://www.ClinicalTrials.gov, as required by U.S. Law. This Web site will not include information that can identify you. At most, the Web site will include a summary of the results. You can search this Web site at any time."

**NIH:** "A description of this clinical trial will be available on http://www.ClinicalTrials.gov. This Web site will not include information that can identify you. At most, the Web site will include a summary of the results. You can search this Wel site at any time."

#### Risks

A. Describe potential research-related risks and discomforts (consider physical, psychological, legal, social/economic/financial, loss of confidentiality, group harms); describe the probability, magnitude, and duration of the potential risks; do not address risks that would be present if the individual did not participate:

Physical risks: The subjects included in this study require VADs for medical treatment, which poses risks for complications and hospital-acquired conditions. Since it is not yet clearly known whether one VAD is more effective than the other in pediatric patients, the research randomization process could introduce physical risks that may not have occurred if the opposite VAD was selected by the medical team.

(1) Based on available literature, LPCs are safer than PICCs with fewer significant side effects (VTE, CLABSI) because they don't enter the central circulation. However, because LPCs are peripheral VADs (similar to a regular peripheral IV) they may not last as long as a PICC. Patients randomized to the LPC arm may be at higher risk for needing VAD replacement due to early catheter failure.

(2) VADs are sometimes used for lab draws to avoid extra poke to the patient. Both PICCs and LPCs can be used for lab draws; however, it is unknown if LPCs can sustain as many lab draws as PICCs before catheter failure.

(3) Most PICCs are placed under sedation while LPCs are placed awake. Randomization to the LPC arm would prevent the risks associated with sedation (e.g., nausea/vomiting, confusion). However, because the LPC will be placed in an awake patient (similar to a regular peripheral IV), there would be pain/discomfort with the placement, but this discomfort would be short lived (most discomfort is while the needle is inserted which takes a few seconds) and minimized using established comfort measures. Any other physical risks are expected to be comparable to ordinary medical care.

Psychosocial risks: Subjects and their guardians may feel discomfort participating in the structured interview about their experience with the VAD. Discomfort could arise from recalling stressful experiences during the child's hospitalization. These risks are expected to be comparable to ordinary life.

Privacy risks: Data security breaches could risk a loss of privacy for subjects included in this study.

